9.2 SAMPLE SIZE DETERMINATION

The purpose of the proposed study is to gather the data required so that effect size estimates may be calculated for each of the study hypotheses. Moreover, there are no published human studies on the effects of tPBM on levels of these biomarkers. Therefore, one of the goals of this study is to obtain a reliable effect size estimate of tPBM on brain function and fluid biomarkers of neurodegeneration, inflammation, and neurotropic factors in anticipation of a larger PBM dementia trial. Power analyses suggest that based on our proposed sample size (8 randomly assigned to tPBM and 8 to sham), at power = .80 and alpha = .05, we will be able to detect evidence of meaningful between-group differences (≥ 0.25 SDs) in the behavioral and biomarker outcome measures.

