1 PROTOCOL SUMMARY

1.1 SYNOPSIS

Title:	Examining the Impact of Photobiomodulation on Cognition, Behavior, and Biomarkers of Alzheimer’s Disease.
Study Description:	The proposed sham-controlled pilot trial will investigate the safety and tolerability of 16 weeks of home transcranial photobiomodulation (tPBM) treatment with commercially available device (i.e., Vielight Neuro Gamma) in 14 patients with mild-to-moderate Alzheimer’s Disease (AD). We will also examine the effects of home PBM on the cognitive function, behavioral symptoms, cerebrospinal fluid and blood biomarkers of AD pathology, including amyloid burden, tangle pathology, axonal injury, microglia activation/inflammation, and neurotrophic factors. We hypothesize that home PBM treatments will be safe and tolerable. We further hypothesize that effect sizes will suggest AD patients randomized to the active PBM condition have improved cognitive function and fewer behavioral symptoms after 16 weeks compared to patients randomized to Sham. Based on reports that PBM upregulates neuroprotective factors, reduces neuroinflammation, induces peripheral and central nerve regeneration, and prevents degeneration, we hypothesize that these behavioral improvements will correlate with changes in fluid biomarkers of neurodegeneration (i.e., neurofilament light chain, NfL) and Alzheimer’s disease (e.g., A β 42 and A β 42/A β 40, total- and phosphorylated-tau).
Objectives:	Primary Objective: Examine the safety and tolerability of home tPBM delivered with a commercially available PBM device. Secondary Objectives: Examine the effects of home tPBM on cognition, behavior, and fluid biomarkers of AD.
Endpoints:	Primary: All adverse events Secondary: Change in ADAS-cog and biochemical biomarkers (A β 40, A β 42, total and phosphorylated tau, NfL)
Study Population:	Men and women, ages 50 years or older with have prodromal, mild or moderate typical or atypical AD, supported by clinical AD biomarkers and a Mini-Metal State Exam (MMSE) score > 13.
Phase or Stage:	1B
Description of Sites/Facilities Enrolling Participants:	San Francisco VA Medical Center and University of California Memory and Aging Center
Description of Study Intervention/Experimental Manipulation:	Transcranial and intranasal photobiomodulation, delivers near-infrared light ($\lambda = 810 \text{ nm}$, 40 Hz, 40-150 mW/cm ²) to the scalp and one nostril.
Study Duration:	36 months
Participant Duration:	4-8 months

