6.3 MEASURES TO MINIMIZE BIAS: RANDOMIZATION AND BLINDING

Subjects will be randomized 1:1 to either tPBM or sham. Study co-investigator ([name]) will provide the randomization list to study staff as eligible participants are enrolled. Blinding will be maintained because the Vielight Neuro Gamma devices use light emitting diodes, and it does not produce heat or noise, and the 810 nm wavelength produces non-visible energy.

[name] will give study staff sealed envelopes with the codes for participant randomizations. The envelopes would be opened only in a situation where an SAE is determined as possibly or potentially related to study intervention. The breaking of the blind will be reported to the IRB, as part of the SAE report.

7 STUDY INTERVENTION/EXPERIMENTAL MANIPULATION DISCONTINUATION AND PARTICIPANT DISCONTINUATION/WITHDRAWAL

Subjects may be withdrawn from the study for any of the following reasons:

1. Subject's or Caregiver's choice to withdraw their consent to participate. Any participant has the right to withdraw from the study at any time and for any reasons without prejudice to future medical care by the physician or the institution. This will be considered a screening failure if they withdraw from the study prior to being randomized. Participants who withdraw consent after randomization will have any available data evaluated, up to the time of withdrawal.
2. Investigator's choice to withdraw the subject from the study. This will be considered a screening failure if the Investigator withdraws the patient prior to randomization.
3. Study termination for either administrative or safety reasons.

For participants who are noncompliant with follow up visits, every effort will be made to collect the data requested by this protocol through the follow up period. All data collected up until the period the subject has withdrawn from the study will be used for this study.

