9.3 STATISTICAL ANALYSES

9.3.1 GENERAL APPROACH

Categorical and continuous demographic and clinical data will be compared between groups with the Fisher's exact or non-parametric Kolmogorov-Smirnov tests. Biomarker data will be inspected for normality with the Shapiro-Wilk test. Associations between clinical and biomarker data will be analyzed with Spearman correlations. Given the exploratory nature of the study, correlations will not be corrected for multiple comparisons and only uncorrected results are presented. Changes in clinical variables and biomarkers will be determined by calculating a change score as the ratio of value at week 16 over the value at baseline. Thus, a change score of 1 will signify no change compared to baseline and change scores < 1 and > 1 reflect, respectively, a decrease or an increase in the neurocognitive or functional scale score or biomarker concentration at week 16, compared to baseline. Between-group change scores will be compared with the non-parametric Kolmogorov-Smirnov tests.

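### Section 9.2 aims for a reliable effect size estimate, but at 8 per arm the 95% interval is about ±1 SD, four times the 0.25 SD the plan calls meaningful

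*Combined protocol and SAP*

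**What the plan says.** Section 9.2 explains that the study is meant to supply data from which effect sizes can be calculated for each hypothesis. Noting that no human data exist on these biomarkers, it names as one goal "to obtain a reliable effect size estimate of tPBM on brain function and fluid biomarkers" and adds "in anticipation of a larger PBM dementia trial". The only quantitative support for the sample size is a power statement: with "8 randomly assigned to tPBM and 8 to sham", "at power = .80 and alpha = .05", the study is said to detect "meaningful between-group differences (≥ 0.25 SDs) in the behavioral and biomarker outcome measures".

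Section 9.2 does not define reliability, and it gives no precision target or expected interval width. Sections 9.3.1 to 9.3.3 do not fill the gap. Change is obtained by "calculating a change score as the ratio of value at week 16 over the value at baseline", and the arms are compared with Kolmogorov-Smirnov tests. No effect-size estimator or confidence interval is named. The synopsis (section 1.1) describes the trial as run "in 14 patients with mild-to-moderate" disease, which at the 1:1 allocation of section 6.3 means 7 per arm instead of 8.

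**The concern.** A pilot may aim at estimation instead of testing, but the relevant property is then the width of the interval. Section 9.2 claims that property without showing it. If the interval covers everything from appreciable harm to a very large benefit, the estimate does not tell a planner whether a larger trial should be small, large or not run at all.

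This is a different defect from the power sentence that follows it. Correcting the power figure would leave the claim of reliability standing, and a reader of the results could still take the point estimates as a sound basis for the next trial.

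**Working it through.** **Inputs.** 8 per arm (section 9.2); 7 per arm from 14 patients at 1:1 (sections 1.1 and 6.3); power 0.80, alpha 0.05 and a meaningful difference of 0.25 SD (section 9.2). The documents give no SD, so all figures are in SD units of the analysed change score. They state no dropout rate; 0% is assumed, which is the best case. Sidedness is not stated; two-sided is used unless noted.

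**1. The plan's own figure.** Two-sample power at 8 per arm for 0.25 SD is 7.2% by the normal approximation (7.5% by t-test), or 12.6% one-sided (12.1%). It is not 80%. Reaching 80% needs 2 × (1.96 + 0.84)² / 0.25² ≈ 251, rounded up to 252 per arm with unrounded z-values (198 one-sided). At 8 per arm, the difference detectable with 80% power is 1.40 SD (z) or 1.51 SD (t). The power sentence therefore does not reproduce and cannot stand in for a precision argument.

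**2. Precision of the estimate.** The standard error of a standardised difference near zero is √(2/n).

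| n per arm | √(2/n) | 1.96 × SE | t-based |
|---|---|---|---|
| 8 | 0.500 | 0.98 | 2.145 × 0.500 = 1.07 |
| 7 | 0.535 | 1.05 | 2.179 × 0.535 = 1.16 |

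Relative to 0.25 SD, these are 0.98/0.25 = 3.9 and 1.07/0.25 = 4.3 at 8 per arm, and 4.2 and 4.7 at 7 per arm.

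Exact 95% intervals (noncentral t) at 8 per arm:

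| Observed d | 95% interval |
|---|---|
| 0 | -0.98 to 0.98 |
| 0.25 | -0.74 to 1.23 |
| 0.5 | -0.51 to 1.49 |
| 0.8 | -0.24 to 1.81 |

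**3. What this would do to a follow-on trial.** Suppose the larger trial were sized by n = 2 × (1.96 + 0.84)² / d², with d the pilot estimate. This rule is an assumption; the documents contain no sizing rule. Because n varies as 1/d², the planned n is within a factor of 2 of the right one only when d lies between the true effect divided by √2 and the true effect times √2. From the noncentral t distribution of d at 8 per arm:

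| Assumed true effect | Wrong sign | n below half | n above double | n within factor 2 |
|---|---|---|---|---|
| 0.25 SD | 31% | 42% | 13% | 14% |
| 0.5 SD | 16% | 35% | 22% | 27% |
| 0.8 SD | 5% | 28% | 26% | 40% |

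The wrong-sign column can be checked by hand: the true effect divided by 0.5 is the z-value, so 0.25 SD gives Φ(-0.5) = 31% and 0.5 SD gives Φ(-1) = 16%. With Hedges' small-sample correction, the last column becomes 14%, 28% and 43%, so the correction does not change the picture.

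**4. Sensitivity to the meaning of SD.** If SD meant the baseline SD, with a simple difference score and an assumed pre-post correlation of 0.8, the SD of change would be √(2 × 0.2) = 0.63 baseline SD. The half-width would be 0.98 × 0.63 = 0.62 to 1.07 × 0.63 = 0.68 baseline SD, still more than twice 0.25. The relative error in the follow-on sample size would not change.

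**The case against.** The fairest defence is that this is a small pilot whose primary objective is safety and tolerability, that section 9.3.1 calls the work exploratory, and that the word *reliable* is loose drafting which changes no visit, analysis or safety procedure. All of that is true and lowers the consequence. It does not supply the missing property, because section 9.2 presents estimation for a larger trial as a reason for doing the study.

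Three stronger readings are tempting, and the documents do not support them.

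- A reader might infer that the sponsor has committed to sizing the next trial from the observed effect, or that this is the main use of the secondary results. Section 9.2 says only that the estimate is one of the goals and is obtained with a larger trial in view. The use is implied, not stated.
- A reader might infer that a trial sized this way would usually be badly wrong. That depends on what counts as badly wrong and on the assumed true effect. With the factor-of-2 criterion, the share of pilots that come close enough rises from 14% at 0.25 SD to 51% at 1.1 SD. If the criterion is instead a wrong sign or follow-on power below 50%, the failing shares are about 71%, 47% and 29% at 0.25, 0.5 and 0.8 SD, so *usually* holds only near 0.25 SD.
- A reader might infer that the next trial would tend to be underpowered because favourable pilots are the ones taken forward. The documents say nothing about such selection. Without it, at a true 0.8 SD and with Hedges' correction, more than doubling the right size (28%) is at least as common as falling below half of it (24%).

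It can also be said that this shares its cause, small n, with the faulty power sentence. It does, and the two edits belong together, but repairing one sentence does not repair the other.

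**Conclusion.** The point holds in this form: section 9.2 claims a property of the estimate that 16 (or 14) patients cannot give, and nothing elsewhere in the document supplies a precision target, estimator or interval that would cure it. The size is a 95% half-width of about 1 SD, roughly four times the plan's own meaningful difference. That finding needs only the stated sample size, complete data and a conventional standardised mean difference; dropout would widen the interval.

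The figure of 14% to 40% within a factor of 2 is conditional on two assumptions: sizing from the point estimate, and true effects of 0.25 to 0.8 SD. It illustrates the consequence and does not describe something the sponsor has said it will do. The primary safety endpoint is unaffected.

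**What to change.** In section 9.2, replace the claim of a reliable estimate with a preliminary estimate, state its expected 95% half-width (about 1 SD at 8 per arm, about 1.05 SD if the total is 14), and say that the point estimate alone is not precise enough to size the larger trial. Make this edit together with the correction of the 0.25 SD power sentence, using whichever total the sponsor confirms.

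Optional advice, since this protocol need not fix how a later trial is planned: size that trial from a minimum important difference together with a conservative SD. One convention is the upper 80% limit, √(df / χ² at 0.20): √(14/9.467) = 1.22 times the pooled SD at 14 df, or √(12/7.807) = 1.24 at 12 df. It assumes normal data, which ratio change scores may not satisfy.

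The cost is a few sentences. Design, enrolment and participant burden do not change. The downside is that a stated goal of the study reads less favourably.

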9.3.3 ANALYSIS OF THE SECONDARY ENDPOINT(S)

Kolmogorov-Smirnov tests will be used to compare clinical and biomarker change scores in the two groups. Associations between clinical and biomarker data will be analyzed with Spearman correlations.

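### Section 9.2 claims 80% power for differences of 0.25 SD with 8 per arm; actual power is about 7.5% by t-test and 3% by the planned Kolmogorov-Smirnov test, and the synopsis gives 14 patients, not 16

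*Combined protocol and SAP*

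**What the plan says.** Section 9.2 holds the plan's only power statement. Taking 8 patients in each arm, 80% power and a 5% alpha, it concludes: "we will be able to detect evidence of meaningful between-group differences (≥ 0.25 SDs) in the behavioral and biomarker outcome measures". It does not give the test, the sidedness, a baseline-to-week-16 correlation, a dropout allowance, or which SD is meant (raw score, change or ratio). The same section says that the purpose is to obtain effect size estimates for a larger trial.

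The analysis sections name the test. Section 9.3.1 defines the change score as the week-16 value divided by the baseline value and says "Between-group change scores will be compared with the non-parametric Kolmogorov-Smirnov tests". Section 9.3.3 repeats this for the secondary endpoints: "Kolmogorov-Smirnov tests will be used to compare clinical and biomarker change scores in the two groups".

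Section 1.1 describes the trial as "in 14 patients with mild-to-moderate" AD. Section 6.3 randomizes 1:1, so 14 would mean 7 per arm. Section 9.2 has 8 per arm, a total of 16.

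**The concern.** With 8 per arm, the standard error of a difference in means is sqrt(2/8) = 0.5 SD. A true difference of 0.25 SD is therefore half a standard error, and no ordinary two-group test has 80% power for that.

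Section 9.1 states directional hypotheses for ADAS-cog, CTT, NPI, ADCS-ADL and NfL, and section 9.3.3 tests the clinical and biomarker changes formally. A reader who trusts section 9.2 could take a non-significant result as evidence against effects of 0.25 SD or more, and could carry that reading into the planning of the larger trial.

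**Working it through.** **Inputs.** 8 per arm, power .80, alpha .05 and 0.25 SD (section 9.2); 1:1 allocation (6.3); Kolmogorov-Smirnov test (9.3.1, 9.3.3); 14 patients, so 7 per arm (1.1). Assumed because not stated: two-sided alpha, normal data with equal SDs and a pure shift, no dropout.

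**1. Attempt to reproduce the stated 80% (t-test).** The noncentrality is 0.25 × sqrt(n/2).
- n = 8: 0.25 × 2 = 0.50 on 14 df, critical t 2.145, power 7.5%.
- n = 7: 0.25 × 1.871 = 0.468 on 12 df, critical t 2.179, power 7.2%.
- One-sided alpha .05 gives 12.1% and 11.4%.

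The stated 80% is not reproduced.

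**2. Sample size for 80% power at 0.25 SD.** The normal approximation is 2 × (1.960 + 0.842)² / 0.25² = 251.2, so 252 per arm; the exact t-test calculation gives 253. Kolmogorov-Smirnov needs about 350 per arm (simulated power 78.9% with 330 and 81.3% with 350).

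**3. The planned test.** With n per arm, the exact null probability of D ≥ k/n in the upper range is 2 × C(2n, n−k) / C(2n, n).
- n = 8: D ≥ 5/8 has p = 2 × 560/12870 = 0.087; D ≥ 6/8 has p = 2 × 120/12870 = 0.0186. The test rejects only at 6/8 or more, so its true level is 1.9%.
- n = 7: D ≥ 5/7 has p = 2 × 91/3432 = 0.053; D ≥ 6/7 has p = 2 × 14/3432 = 0.0082. The true level is 0.8%.

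Power of the exact test comes from simulation (at least 200,000 trials per point).

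| Two-sided alpha .05 | 8 per arm | 7 per arm |
|---|---|---|
| t-test power at 0.25 SD | 7.5% | 7.2% |
| t-test power at 1.0 SD | 46% | 41% |
| Exact K-S power at 0.25 SD | 2.9% | 1.3% |
| Exact K-S power at 1.0 SD | 23% | 12% |
| Exact K-S power at 1.5 SD | 52% | 32–33% |
| 80% power reached at, t-test | 1.51 SD | 1.63 SD |
| 80% power reached at, exact K-S | about 2.0 SD | about 2.45 SD |

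With 8 per arm, 1.51/0.25 = 6.0 and 2.0/0.25 = 8.0 times the stated difference.

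**4. Readings that might rescue the figure.**
- *Baseline adjustment.* The standardized effect becomes 0.25/sqrt(1 − ρ²). Setting this to 1.507, the t-test's 80% value, gives ρ² = 1 − (0.25/1.507)² = 0.9725, so ρ is about 0.986. A simple difference from baseline, 0.25/sqrt(2(1 − ρ)), needs the same 0.986. At ρ = 0.8, adjusted power is 12.2%.
- *0.25 as Cohen's f for a group-by-time interaction.* With N = 16 and two time points, λ = 0.25² × 16 × 2/(1 − ρ) = 2/(1 − ρ). Power is 46% at ρ = 0.5, 80% at 0.78 and 83.6% at 0.80. But f = 0.25 in that model is a between-arm difference in change of 4 × 0.25 = 1.0 SD, not 0.25 SD, and the plan contains no such analysis.

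**5. Precision.** The expected 95% CI half-width for an unadjusted mean difference is t(0.975, 2n−2) × sqrt(2/n): 2.145 × 0.5 = 1.07 SD with 8 per arm, and 2.179 × 0.5345 = 1.16 SD with 7.

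**The case against.** **This is a pilot.** The primary endpoint is adverse events, section 9.2 puts effect size estimation first, section 9.3.1 calls the study exploratory, and no decision rule depends on the 0.25 SD figure. All of that is true, and it limits the consequence to the secondary comparisons. It does not make a specific power figure correct.

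**The Kolmogorov-Smirnov figures depend on how the p-value is computed**, which the plan does not say. The plain asymptotic p-value at D = 5/8 is 0.088 and does not reject. A small-sample-corrected asymptotic p-value is 0.0497 and does. With that version and 8 per arm, power is about 11% at 0.25 SD, 49% at 1.0 SD and 79% at 1.5 SD, and 80% is reached near 1.5 SD. But D ≥ 5/8 has a true null probability of 8.7%, so that version does not hold the stated alpha .05, and 11% is still far from 80%. What stands is that every Kolmogorov-Smirnov figure should be labelled as exact.

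**The planned score is a ratio**, and normality of a ratio is an assumption. This is fair. The test uses only the ordering of the values, so the same figures apply if the log ratio is normal and the shift is in SDs of the log ratio. Other shapes could move them, but 80% at 0.25 SD is not plausible.

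**The plan has no confidence interval for a mean difference.** Also fair: the half-width should be offered as an illustration of precision only.

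**Conclusion.** The concern holds. The power stated in section 9.2 is wrong by about a factor of ten against a t-test (80% against 7.5%) and by more against the test the plan names. With 8 per arm, the exact Kolmogorov-Smirnov test would miss a true 0.25 SD effect about 97% of the time and a true 1.0 SD effect about 77% of the time. These figures rest on the assumptions listed with the inputs; dropout would lower power further. No choice of sidedness, p-value method or plausible baseline correlation brings the claim near 80%.

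The totals of 14 and 16 are a separate inconsistency. The documents do not show which is intended, for example as randomized against completing patients. With 14, every figure is worse. The adverse-event primary endpoint is not affected.

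**What to change.** Delete the 0.25 SD power sentence in section 9.2 and replace it with wording such as:

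> With 8 patients per arm and two-sided alpha 0.05, the planned exact Kolmogorov-Smirnov test has 80% power only for differences of about 2.0 SD of the analysed change score (for reference, a two-sample t-test: about 1.5 SD), assuming normal data and no dropout. As an illustration of precision, the expected 95% CI half-width for an unadjusted mean difference is about 1.1 SD. Secondary results are estimates with wide uncertainty, and non-significance does not exclude meaningful effects.

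Use one sample size in sections 1.1 and 9.2. If it is 14 (7 per arm), the figures become about 2.4 to 2.5 SD (exact Kolmogorov-Smirnov), 1.6 SD (t-test) and 1.2 SD (half-width). State in section 9.3.1 that Kolmogorov-Smirnov p-values are exact.

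The cost is protocol wording and a less favourable stated detectable difference. No patients are added, and the primary endpoint does not change.

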9.3 STATISTICAL ANALYSES

9.3.1 GENERAL APPROACH

Categorical and continuous demographic and clinical data will be compared between groups with the Fisher's exact or non-parametric Kolmogorov-Smirnov tests. Biomarker data will be inspected for normality with the Shapiro-Wilk test. Associations between clinical and biomarker data will be analyzed with Spearman correlations. Given the exploratory nature of the study, correlations will not be corrected for multiple comparisons and only uncorrected results are presented. Changes in clinical variables and biomarkers will be determined by calculating a change score as the ratio of value at week 16 over the value at baseline. Thus, a change score of 1 will signify no change compared to baseline and change scores < 1 and > 1 reflect, respectively, a decrease or an increase in the neurocognitive or functional scale score or biomarker concentration at week 16, compared to baseline. Between-group change scores will be compared with the non-parametric Kolmogorov-Smirnov tests.

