8 STUDY ASSESSMENTS AND PROCEDURES

8.1 ENDPOINT AND OTHER NON-SAFETY ASSESSMENTS

Cognitive and Behavioral Outcome Measures will be assessed at baseline and after 16 weeks by a study staff member who will be blind to treatment assignment. The measures are standard in the field and have well-established validity and reliability:

- The **Mini-Mental State Exam (MMSE)** (Folstein et al., 1975) is a fully structured screening instrument frequently used for Alzheimer’s disease drug studies. The scale evaluates orientation, memory, attention, concentration, naming, repetition, comprehension, and ability to create a sentence and to copy two overlapping pentagons.
- The **Alzheimer’s Disease Assessment Scale, Cognitive Subscale (ADAS-cog)** (Rosen et al., 1984) is a structured scale that evaluates memory (word recall, word recognition), reasoning (following commands), language (naming, comprehension), orientation, ideational praxis (placing letter in envelope) and constructional praxis (copying geometric designs). Ratings of spoken language, language comprehension, word finding difficulty, and ability to remember test instructions are also obtained. The test is scored in terms of errors, with higher scores reflecting poorer performance. Scores can range from 0 (best) to 70 (worse).
- The **Color Trails Test (CTT)** (D’Elia et al., 1996) is a non-verbal test of visual attention, graphomotor sequencing, and effortful executive processing abilities (i.e., sustained attention and set shifting).
- The **Neuropsychiatry Inventory (NPI)** (Cummings, 1997) is a well-validated, reliable, multi-item instrument to assess psychopathology in AD based on an interview with a study companion or qualified partner.
- The **Alzheimer’s Disease Cooperative Study, Activities of Daily Living (ADCS-ADL)** (Galasko et al., 1997) assesses the competence of patients with AD in basic and instrumental activities of daily living (ADLs). It can be completed by a caregiver in questionnaire format, or administered by a clinician/researcher as a structured interview with a caregiver.

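### Secondary outcomes are compared between arms only by Kolmogorov-Smirnov tests on unadjusted ratios, so the plan names no effect estimate or interval although effect sizes are the pilot's stated purpose

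*Combined protocol and SAP*

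**What the plan says.** The Synopsis (1.1) frames the efficacy hypothesis as an expectation that "effect sizes will suggest AD patients randomized to the active PBM condition have improved cognitive function and fewer behavioral symptoms" relative to sham. Section 9.2 says the study gathers data so that "effect size estimates may be calculated for each of the study hypotheses", and names as one goal to "obtain a reliable effect size estimate of tPBM on brain function and fluid biomarkers" ahead of a larger trial. Section 9.1 puts ADAS-cog, CTT, NPI, ADCS-ADL and NfL in the secondary hypotheses. Sections 1.1 and 3 list ADAS-cog and the biomarkers as secondary endpoints.

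Section 9.3.1 defines change for both clinical variables and biomarkers by "calculating a change score as the ratio of value at week 16 over the value at baseline", then states: "Between-group change scores will be compared with the non-parametric Kolmogorov-Smirnov tests". Section 9.3.3 repeats this: "Kolmogorov-Smirnov tests will be used to compare clinical and biomarker change scores in the two groups". The only other analysis of these outcomes in 9.3.1, 9.3.3 and 9.3.6 is association between clinical and biomarker data by Spearman correlation, which does not contrast the arms. Section 8.1 says of the scales: "Cognitive and Behavioral Outcome Measures will be assessed at baseline and after 16 weeks". The baseline needed for adjustment is therefore collected.

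**The concern.** The stated purpose is estimation, but the stated analysis is a test. The two-sample KS statistic is the largest vertical gap between two empirical distribution functions. In its two-sided form it has no sign, it is not in scale points or SD units, and it cannot size a later trial. Sections 9.3.1 to 9.3.6 name no mean or median difference, ratio of means, standardised difference, model, covariate or confidence interval.

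The gap covers NfL and the other biomarkers as well as the clinical scales. A ratio is a reasonable scale for a concentration, but a KS test on it still yields no estimate.

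Two things are at stake. If effect sizes are worked out later from the raw scores, the choices (points or ratio, adjusted or not, which SD) will be made after the data are seen. And without an interval, readers of the pilot will not see how little 7 or 8 patients per arm can say.

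**Working it through.** **Inputs.** Per-arm size: the Synopsis gives 14 patients (7 per arm at the 1:1 allocation of Section 6.3), and Section 9.2 gives 8 and 8. Both are carried through. Alpha 0.05 and a difference of 0.25 SD come from Section 9.2, which does not define that SD. The ADAS-cog runs from 0 to 70, higher being worse (Section 8.1). All other inputs below are assumptions and are labelled as such.

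**1. The plan's own figure.** Section 9.2 claims 80% power for 0.25 SD with 8 per arm. For a two-sided t test the noncentrality is 0.25 × √(8/2) = 0.50 on 14 df, which gives power of 7.5% (7.2% with 7 per arm). The figure does not reproduce. That is a separate point. It matters here only because 0.25 SD is the plan's benchmark for precision.

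**2. True size of KS.** Enumerating all equally likely allocations without ties:

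| Per arm | Allocations | D | Allocations with at least this D | Exact p |
|---|---|---|---|---|
| 7 | 3,432 | 5/7 | 182 | 0.053 |
| 7 | 3,432 | 6/7 | 28 | 0.008 |
| 8 | 12,870 | 5/8 | 1,120 | 0.087 |
| 8 | 12,870 | 6/8 | 240 | 0.019 |

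The smallest D that rejects at 0.05 is 6/7 or 6/8, so the true size is 0.8% or 1.9%.

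**3. Precision of a baseline-adjusted difference.** With balanced baselines the 95% half-width in residual SD is t × √(2/n):

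- 7 per arm: t(11) = 2.201, and 2.201 × √(2/7) = 1.18
- 8 per arm: t(13) = 2.160, and 2.160 × √(2/8) = 1.08

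Allowing for chance baseline imbalance and an estimated residual SD (200,000 simulated trials), the means are 1.20 and 1.10.

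On an assumed ADAS-cog-like scale (baseline mean 20, SD 10, floor 3; change SD 5; drift +1; week 16 held to 0–70), 20,000 simulated trials give mean half-widths of about 5.9 points (7 per arm) and 5.4 points (8 per arm). Divided by each trial's own pooled baseline SD, these are roughly 0.65 and 0.59. That is a little more than 5.9/10 and 5.4/10, because the floor shrinks the SD and because a small-sample SD is the divisor.

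Against 0.25: 0.65/0.25 = 2.6 and 0.59/0.25 = 2.4 if the SD of Section 9.2 is the baseline SD; 1.20/0.25 = 4.8 and 1.10/0.25 = 4.4 only if it is the residual SD.

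**4. Where power is lost.** Same model, assumed 8-point effect:

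| Per arm | KS on ratio | ANCOVA held to the KS size | ANCOVA at 5% |
|---|---|---|---|
| 7 | 34.5% | 41.1% | 73.8% |
| 8 | 53.8% | 64.3% | 80.6% |

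Share of the gap due to KS conservatism: (73.8 − 41.1)/(73.8 − 34.5) = 83%, and (80.6 − 64.3)/(80.6 − 53.8) = 61%. Under an assumed proportional 40% benefit, KS on the ratio has 37.6% and 58.5% power, against 31.3% and 55.7% for ANCOVA held to the same size.

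**5. How intervals behave.** In the 8-point example the ANCOVA interval in points covers about 95%. Dividing its limits by the sample baseline SD gives an interval that covers only about 91–92%, because that SD is itself estimated. For an NPI-like skewed count (assumed negative binomial, treatment halving the mean), ANCOVA interval coverage falls to 90–92%.

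**The case against.** This is a small phase 1B pilot with a safety primary endpoint. KS is a valid distribution-free test, and Section 9.2 promises only to gather data from which effect sizes can be calculated. Raw scores are collected, so that remains possible. ANCOVA is also one choice among several: a Hodges-Lehmann shift with its interval would close the gap and stay within the plan's non-parametric approach.

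Most of this stands, and it limits the point without removing it. The data will exist, but the estimator is not pre-specified, and for a pilot meant to supply effect sizes the estimate and its interval are the product. The exploratory label in Section 9.3.1 is used only to waive multiplicity correction for the correlations.

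A reader might infer more than the documents support:

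- *That the test is invalid.* It errs on the conservative side, so type I error is not inflated.
- *That the ratio is what costs power.* Most of the gap in the example is KS discreteness, and under a proportional benefit the ratio does no worse.
- *That intervals would be four to five times the planned 0.25 SD.* That needs the residual SD, and Section 9.2 does not say which SD it means.
- *That zero baselines break the analysis.* No rule is given for them, but this is minor: zero is unlikely on the ADAS-cog here, the documents give no NPI range, and only 0/0 cannot be ranked.

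**Conclusion.** The point holds on the text alone. The plan makes effect sizes its purpose, and its between-arm analysis of the clinical scales and biomarkers, NfL included, yields none. No simulation is needed for that.

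The size of the issue has two parts. KS at nominal 5% operates at 0.8% or 1.9%; this is exact, assuming no ties. The imprecision that would go unreported is about ±1.20 or ±1.10 residual SD. In the assumed example that is more than twice 0.25 if Section 9.2 means the baseline SD. The point and power figures rest on the assumed ADAS-cog-like model.

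The primary safety endpoint is not analysed as a ratio and is outside this point. The change should be made before unblinding, but it does not bear on participant safety.

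**What to change.** In Sections 9.3.1 and 9.3.3, replace KS as the main between-arm analysis with the following:

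- **ADAS-cog, CTT, NPI, ADCS-ADL:** the difference in mean week-16 score, tPBM minus sham, from a linear model with treatment and baseline score, with its 95% CI in the units of the scale. No rule for zero baselines is then needed.
- **Skewed scales such as NPI and CTT:** in addition, a rank-based shift (for example Hodges-Lehmann) with its own interval, or an interval from inverting a permutation test. A permutation p-value alone gives no interval.
- **NfL and the other biomarkers:** a baseline-adjusted geometric mean ratio, from the same model on the log scale, with its 95% CI.
- **Any standardised effect:** name the SD used, and use an interval that allows for its estimation (bootstrap or noncentral-t based). Do not say that it matches Section 9.2 unless that section is amended to define its SD.
- **KS on the ratio:** may stay as description.

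The cost is analysis-plan wording. Baseline and week-16 values are already scheduled (Sections 1.3 and 8.1), so no visits, assays or patients are added. The downside to state openly is a model assumption in a very small sample, and visibly wide intervals.
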